8.3 STATISTICAL ANALYSES

8.3.1 GENERAL APPROACH

Data will be exported from REDCap to IBM SPSS statistical software, Version 25 and standard data cleaning procedures will be completed. Study variables for the entire sample will be examined using descriptive statistics such as frequencies and percentages (for categorical variables) and means, standard deviations, percentiles, and ranges (for continuous variables) to ensure values are reasonable. Prior to conducting analyses related to the hypotheses of the study, individual distributions of continuous variables will be examined visually with histograms to confirm that all assumptions for the analyses are reasonably met. Methods robust to distributional assumptions will be used as appropriate. The impact of incorrect data entry will be minimized by the implementation of logic checks in the entry forms on REDCap.

Data analysis for between-group comparisons will begin with descriptive statistics for baseline participant characteristics and outcomes by treatment group. Balance between groups will be assessed using measures of effect size such as the standardized mean difference (Cohen's d) for continuous variables and d -equivalent for binary or categorical variables. Patterns of missing data will be examined according to baseline covariates. Baseline factors that could be causally related to the outcomes and showing relevant between group imbalances or that are predictive of missing data will be used as adjusting covariates. Mixed-effect modeling techniques and covariate adjustment will reduce the impact of missing data, as

the approach allows for using all collected data, and the missing data are considered missing conditionally (on the covariates) at random, a milder assumption than missing completely at random.

8.3.2 ANALYSIS OF THE PRIMARY EFFICACY ENDPOINT(S)

Measures of effect size and tests of between group differences (e.g., t-tests, chi-squared tests) will be conducted to compare groups. An FDR approach will be used to adjust for multiple exploratory inferences.

8.3.3 ANALYSIS OF THE SECONDARY ENDPOINT(S)

Generalized linear mixed-effects models with random effects for subject (and logit links for binary outcomes) will be fitted to the repeated measures data. Linear contrasts will be used to estimate between-group differences. Inverse-link estimates will be computed to facilitate interpretation. A false discovery rate (FDR) approach will be considered to adjust for multiple inferences if necessary. Confidence intervals (possibly adjusted for multiple inferences) will be computed to quantify uncertainty about estimates.

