8.2 SAMPLE SIZE DETERMINATION

We propose to recruit 80 participants to the training portion of the study over a 12-month period. Sample size was determined by feasibility, since the primary outcomes of the study are feasibility and acceptability of remote OEND. Feasibility and acceptability are operationally defined as 1) recruitment of 80 participants during the first 12 months of the project; 2) increase in opioid knowledge post-training; 3) 80% completion of assessment measures and 4) 80% endorsement of high scores on a participant satisfaction measure. An exploratory aspect of the study involves determining the occurrence of naloxone kit use and outcomes, though the study will not be powered to evaluate this and will serve as a pilot for a larger study. The fundamental purpose of the proposed pilot study is to assess feasibility and acceptability to inform future studies, not to provide sample size estimates. If testing is conducted, assuming recruitment of 80 participants with a dropout rate of 20% (consistent with prior studies), uniformly distributed over the 3-month follow-up period would result in approximately 70 participants on average at each of the three follow-up time points. The sample size provides 80% power to detect a time-averaged mean difference of .55 SD between groups for a continuous outcome, or an odds ratio of 2.69 for a binary outcome, assuming an alpha level of .05 and an intrasubject correlation of .5 (computations in PASS 11 software).

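### Binary secondary outcomes: the inverse link applied to the subject-random-effect logit model gives the probability at random effect zero, which is not the arm proportion

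*Combined protocol and SAP*

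**What the plan says.** Section 8.3.3 names the model for the repeated follow-up data: "Generalized linear mixed-effects models with random effects for subject (and logit links for binary outcomes) will be fitted to the repeated measures data". Between-group differences then come from linear contrasts, and the section continues: "Inverse-link estimates will be computed to facilitate interpretation". Confidence intervals are planned as well.

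Nothing in sections 8.3.1 to 8.3.3 says whether the back-transformed values are averaged over the random effect, labelled as subject-specific, or paired with a marginal estimate.

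Three other places bear on the point:

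- Section 8.2 bases its power statement on "an intrasubject correlation of .5". It gives no scale for that correlation when the outcome is binary, and no event rates.
- Section 8.3.1 plans descriptive outcomes by treatment group. It also relies on the mixed model and covariate adjustment to justify a missing-at-random assumption conditional on covariates.
- Section 8.1 judges the no-difference part of Hypothesis 3 on point estimates of effect size, without naming the effect measure.

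**The concern.** In a logit model with a subject random intercept, the fixed effects describe a participant at a given value of that intercept. Applying the inverse logit to the fixed-effect predictor sets the intercept to zero. The arm proportion is the average of the inverse logit over all participants. Because the inverse logit is curved, that average is pulled towards 50% relative to the value at zero.

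The back-transformed figures exist to help readers, and a percentage printed beside each arm will be read as that arm's rate. Several follow-up items are yes/no (kit use, overdose, treatment entry, current illicit use). For an uncommon outcome the printed percentage would be too low, and for a common one too high. The difference between two such percentages would not be the risk difference between the arms. That matters in a trial that judges part of Hypothesis 3 on the size of point estimates.

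**Working it through.** **1. The plan's own figures.** Section 8.2 states: "The sample size provides 80% power to detect a time-averaged mean difference of .55 SD between groups for a continuous outcome", and gives "an odds ratio of 2.69 for a binary outcome", with "approximately 70 participants on average at each of the three follow-up time points". I took 35 per arm, m = 3 visits, correlation ρ = .5 and alpha .05, two-sided by assumption.

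- Variance factor: (1 + (m − 1)ρ)/m = (1 + 2 × .5)/3 = 0.667.
- Detectable difference: (1.960 + 0.842) × √(2 × 0.667/35) = 0.547 SD, against .55 stated. Power at .55 SD is 80.4%.
- Odds ratio by conversion: exp(0.547 × π/√3) = 2.696, against 2.69 stated. Direct binomial formulas at 35 per arm give about 2.95 or more.

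The power statement reproduces. The binary figure looks like a conversion from the continuous one, so .5 need not have been meant as a logit-scale quantity.

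**2. Model for the check.** logit(p) = η + u, with u normal, mean 0 and SD σ.

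- Arm proportion: the mean of expit(η + u) over u, by 120-point Gauss-Hermite quadrature.
- Plain inverse link: expit(η).
- Latent intraclass correlation (ICC): σ²/(σ² + π²/3), so σ = √[(ICC/(1 − ICC)) × π²/3]. This gives σ = 0.60, 1.19 and 1.81 for ICC .1, .3 and .5.

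For each true arm proportion I solved for η and then took expit(η). For example, at σ = 1.81 an arm proportion of 20% needs η = −2.108, and expit(−2.108) = 10.8%.

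**3. Rates shown by the plain inverse link.**

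| True arm proportion | ICC .1 | ICC .3 | ICC .5 |
|---|---|---|---|
| 10% | 8.8% | 6.3% | 3.8% |
| 20% | 18.4% | 14.9% | 10.8% |
| 50% | 50% | 50% | 50% |
| 80% | 81.6% | 85.1% | 89.2% |
| 90% | 91.2% | 93.7% | 96.2% |

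**4. Risk differences.** I used the plan's odds ratio of 2.69 as a ratio between arm proportions, with illustrative lower rates of 10% and 20%. Odds of 0.1111 × 2.69 = 0.299 give 23.0%. Odds of 0.25 × 2.69 = 0.6725 give 40.2%.

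| True arms (difference) | ICC .1 | ICC .3 | ICC .5 |
|---|---|---|---|
| 10% and 23.0% (13.0 points) | 12.6 | 11.6 | 9.8 |
| 20% and 40.2% (20.2 points) | 21.0 | 22.7 | 24.2 |

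At ICC .5 the pairs shown are 3.8% and 13.6%, and 10.8% and 35.0%. The first difference narrows and the second widens, so no single direction of correction applies.

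**The case against.** The strongest reply is that the plan does not commit the error. Section 8.3.3 never calls the back-transformed values arm rates, never says they are taken at random effect zero, and does not rule out averaging. The value at zero is a legitimate quantity if labelled. How the software forms its estimated means is not described and was not checked. This stands to the extent that the outcome is not certain. But the sentence as written describes a plain inverse link, and no other text redirects it.

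The formal inference is sound: tests and odds ratios on the logit scale are valid, and continuous outcomes are not touched. This stands in full.

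Observed proportions by arm will be available from the descriptive summaries in section 8.3.1, so a discrepancy could be noticed. This softens the point without removing it, because raw proportions lack the covariate adjustment and missing-data handling for which the model was chosen.

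Three stronger readings are tempting, and the documents do not support them:

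- *Hypothesis 3 will be decided on distorted risk differences.* No risk difference or back-transformed rate is named as the effect measure. Section 8.2 uses an odds ratio and an SD difference. Section 8.3.1 uses Cohen's d and an equivalent, for baseline balance.
- *A larger trial would be sized from wrong rates.* Section 8.2 says the pilot is not meant to supply sample size estimates.
- *The plan's correlation of .5 fixes the gap as large.* Its scale for binary outcomes is not stated. At a latent ICC of .1 the gap is minor.

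**Conclusion.** The point holds for binary secondary outcomes. Followed literally, section 8.3.3 produces percentages that lie further from 50% than the arm proportions whenever the random-effect variance is above zero and the proportion is not 50%. Differences between those percentages can be wider or narrower than the true risk difference. If the .5 in section 8.2 is a latent-scale ICC, a true 20% would show as about half its size; at ICC .1 the shift is between one and two points at 10% and 20%.

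The size rests on a normal random intercept, illustrative arm proportions and an assumed logit-scale variance, none of which the documents give. This is a reporting fault in a secondary analysis. It does not invalidate the model or its tests. It is more than missing detail, because a better summary is available from the same fitted model at little cost.

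**What to change.** Amend section 8.3.3 to say that, for binary outcomes:

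- arm proportions and between-arm risk differences will be population-averaged, by integrating the inverse link over the fitted random-effect distribution of the planned mixed model, and over the observed covariates where the model is adjusted;
- each will carry a 95% confidence interval;
- any probability taken at random effect zero will be labelled subject-specific.

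Keep the mixed model. Replacing it with unweighted generalized estimating equations would also give marginal rates, but would weaken the missing-data assumption on which section 8.3.1 relies, with 20% dropout expected in section 8.2.

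The cost is a sentence or two in the plan and a little programming. The averaged estimates depend on the fitted random-effect variance and on its normality. With three binary responses per participant that variance will be imprecisely estimated, so it should be reported beside the results, and the raw proportions by arm shown with them. The design, sample size and data collection do not change.

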9 SUPPORTING DOCUMENTATION AND OPERATIONAL CONSIDERATIONS

9.1 REGULATORY, ETHICAL, AND STUDY OVERSIGHT CONSIDERATIONS

9.1.1 INFORMED CONSENT PROCESS

9.1.1.1 CONSENT/ASSENT AND OTHER INFORMATIONAL DOCUMENTS PROVIDED TO SUBJECTS

Consent forms describing in detail the study intervention, study procedures, and risks are given to the subject and written documentation of informed consent is required prior to conducting study screening procedures. A separate screening consent form will not be used.

9.1.1.2 CONSENT PROCEDURES AND DOCUMENTATION

Informed consent is a process that is initiated prior to the individual's agreeing to participate in the study and continues throughout the individual's study participation. Consent forms will be Institutional Review Board (IRB)-approved and the subject will be asked to read and review the document. The investigator will explain the research study to the subject and answer any questions that may arise. A verbal explanation will be provided in terms suited to the subject's comprehension of the purposes, procedures, and potential risks of the study and of their rights as research subjects. Subjects will have the opportunity to carefully review the written consent form and ask questions prior to signing. The subjects should have the opportunity to discuss the study with their family or surrogates or think about it prior to agreeing to participate. The subject will sign the informed consent document prior to any procedures being done specifically for the study. Subjects must be informed that participation is voluntary and that they may withdraw from the study at any time, without prejudice. A copy of the informed consent document will be given to the subjects for their records. The informed consent process will be conducted and documented in the source document (including the date), and the form signed, before the subject undergoes any study-specific procedures. The rights and welfare of the subjects will be protected by

emphasizing to them that the quality of their medical care will not be adversely affected if they decline to participate in this study.

9.1.2 STUDY DISCONTINUATION AND CLOSURE

This study may be temporarily suspended or prematurely terminated if there is sufficient reasonable cause. Written notification, documenting the reason for study suspension or termination, will be provided by the suspending or terminating party to regulatory authorities. If the study is prematurely terminated or suspended, the Principal Investigator (PI) will promptly inform study subjects and the Institutional Review Board (IRB), will provide the reason(s) for the termination or suspension. Study subjects will be contacted, as applicable, and be informed of changes to study visit schedule.

Circumstances that may warrant termination or suspension include, but are not limited to:

- Determination of unexpected, significant, or unacceptable risk to subjects
- Demonstration of efficacy that would warrant stopping
- Insufficient compliance to protocol requirements
- Data that are not sufficiently complete and/or evaluable
- Determination that the primary endpoint has been met
- Determination of futility

Study may resume once concerns about safety, protocol compliance, and data quality are addressed, and satisfy the IRB.

9.1.3 CONFIDENTIALITY AND PRIVACY

Subject confidentiality and privacy is strictly held in trust by the participating investigators and their staff. Therefore, the study protocol, documentation, data, and all other information generated will be held in strict confidence. No information concerning the study or the data will be released to any unauthorized third party without prior written approval of the Principal Investigator.

All research activities will be conducted in as private a setting as possible.

Representatives of the Institutional Review Board (IRB) may inspect all documents and records required to be maintained by the investigator, including but not limited to, medical records (office, clinic, or hospital) and pharmacy records for the subjects in this study. The clinical study site will permit access to such records.

The study subject's contact information will be securely stored at each clinical site for internal use during the study. At the end of the study, all records will continue to be kept in a secure location for as long a period as dictated by the reviewing IRB and/or Institutional policies.

Study subject research data, which is for purposes of statistical analysis and scientific reporting, will be stored at the UAB Department of Otolaryngology research office. This will not include the subject's contact or identifying information. Rather, individual subjects and their research data will be identified by a unique study identification number. The study data entry and study management systems used by research staff will be secured and password protected.

9.1.4 QUALITY ASSURANCE AND QUALITY CONTROL

The site will perform internal quality management of study conduct, data collection, documentation and completion. Quality control (QC) procedures will be completed by the Data Manager during data entry into the appropriate CRF. Any missing data or data anomalies will be communicated to the Study Coordinator for clarification/resolution.

Following written Standard Operating Procedures (SOPs), the monitors will verify that the clinical trial is conducted, and data are generated, collected, documented (recorded), and reported in compliance with the protocol, International Conference on Harmonisation Good Clinical Practice (ICH GCP), and applicable regulatory requirements.

The site will provide direct access to all trial related sites, source data/documents, and reports for the purpose of monitoring and inspection by local and regulatory authorities.

9.1.5 DATA HANDLING AND RECORD KEEPING

9.1.5.1 DATA COLLECTION AND MANAGEMENT RESPONSIBILITIES

Data collection is the responsibility of the clinical trial staff at the site under the supervision of the Principal Investigator. The Principal Investigator is responsible for ensuring the accuracy, completeness, legibility, and timeliness of the data reported.

9.1.5.2 STUDY RECORDS RETENTION

Study documents should be retained for a minimum of 3 years after the completion of the study. These documents should be retained for a longer period, however, if required by local regulations.

9.1.6 PROTOCOL DEVIATIONS

A protocol deviation is any noncompliance with the clinical trial protocol requirements. The noncompliance may be either on the part of the subject, the investigator, or the study site staff. As a result of deviations, corrective actions are to be developed by the site and implemented promptly.

These practices are consistent with ICH GCP:

- 4.5 Compliance with Protocol, sections 4.5.1, 4.5.2, and 4.5.3
- 5.1 Quality Assurance and Quality Control, section 5.1.1
- 5.20 Noncompliance, sections 5.20.1, and 5.20.2.

It is the responsibility of the Principal Investigator to use continuous vigilance to identify and report deviations within 10 working days of identification of the protocol deviation. Protocol deviations must be sent to the reviewing Institutional Review Board (IRB) per their policies. The Principal Investigator is responsible for knowing and adhering to the reviewing IRB requirements.

9.1.7 CONFLICT OF INTEREST POLICY

The independence of this study from any actual or perceived influence, such as by the pharmaceutical industry, is critical. Therefore, any actual conflict of interest of persons who have a role in the design, conduct, analysis, publication, or any aspect of this trial will be disclosed and managed. Furthermore, persons who have a perceived conflict of interest will be required to have such conflicts managed in a way that is appropriate to their participation in the design and conduct of this trial.

9.2 ABBREVIATIONS

AE	Adverse Event
ANCOVA	Analysis of Covariance
CFR	Code of Federal Regulations
CONSORT	Consolidated Standards of Reporting Trials
CRF	Case Report Form
DHHS	Department of Health and Human Services
GCP	Good Clinical Practice
HIPAA	Health Insurance Portability and Accountability Act
ICH	International Conference on Harmonisation
ICMJE	International Committee of Medical Journal Editors
IRB	Institutional Review Board
LSMEANS	Least-squares Means
NCT	National Clinical Trial
NIH	National Institutes of Health
OHRP	Office for Human Research Protections
PI	Principal Investigator
QA	Quality Assurance
QC	Quality Control
SAE	Serious Adverse Event
SAP	Statistical Analysis Plan
SOA	Schedule of Activities
SOP	Standard Operating Procedure
UP	Unanticipated Problem
US	United States

